8.3. Data Management

Data must be entered on paper via the CRF booklet or directly on the online E-MOTIVE database (<https://bctu-redcap.bham.ac.uk/>). Where Paper Case Report Forms (CRFs) are completed, these will be signed and dated, filed in the medical records, and data will be entered on to the online E-MOTIVE database by a member of the research team at the local spoke health facilities.

Participating health facility teams should transfer all data from paper CRF booklets into the online E-MOTIVE database. E-MOTIVE Hub research staff will check all electronic CRFs for completeness, data consistency and compliance with the protocol. If discrepancies or missing data are identified, the Hub will raise queries with the research team at the spoke facility via the E-MOTIVE database.

The central E-MOTIVE trial office at BCTU will liaise directly with each Hub to resolve any inconsistencies in data, identified centrally.

8.4. Data Security and data protection

The security of the Trial Database System is governed by the policies of the University of Birmingham. Data management and data security within BCTU will abide by the requirements of the General Data Protection Regulations (GDPR) and any subsequent amendments. The trial will be conducted at collaborating sites in accordance with the country-specific data protection requirements. Data will be acquired and stored on the REDCap platform. Access to data will be

restricted by usernames and passwords, at participating health facilities, Hubs, and BCTU. Each record on the database will be allocated a unique trial number at entry in the database. All documents will use this as the identifier. All data will be analysed and reported in summary format. No individual will be identifiable.

8.5. Archiving

All records created by following trial procedures and all documents listed in guidance relating to the conduct of the trial must be retained and archived. Archiving will be authorised by the BCTU on behalf of the Sponsor following submission of the end of trial report. It is the responsibility of the National Principal Investigator and Local Champion to ensure all essential trial documentation and source documents at their site are securely retained in line with the relevant national laws and regulations. The final dataset will be stored for at least 10 years in accordance with UK Policy Framework for Health and Social Care Research 2017. No documents should be destroyed without prior approval from the BCTU.

9. QUALITY CONTROL AND QUALITY ASSURANCE

9.1. Site Set-up and Initiation

Staff at participating health facilities will undergo a standardised site set-up training package. This will include:

- Online training modules (set-up, control, intervention). Templates will be provided and stored in the Investigator Site Files. Ongoing training will be documented and monitored throughout the study to ensure the intervention is delivered optimally.
- Site initiation visit: from either BCTU or local Hub. Key members of the health facility research team will be required to attend either a meeting or video/teleconference covering aspects of the trial design, protocol procedures, data reporting and record keeping. The BCTU must be informed immediately of any change in the Site research team.
- A two-month E-MOTIVE ‘transition phase’ to allow health facilities to adjust to change clinical practice for the delivery of the interventions.

Site opening

Hubs - Hubs are the central, country-specific coordinating centres (**Figure 6**). The Hubs will take responsibility for the management of the health facilities in the country called the Spoke facilities; will provide administrative services for the country network; will provide training for Spokes and will maintain regular communication with the University of Birmingham. Hubs will sign a contract with the University of Birmingham delineating the responsibilities of the Hub as lead site for the E-MOTIVE trial. Hubs should subsequently put agreements in place with each of the Spoke facilities (if required) and ensure that the necessary approvals are in place prior to commencing the trial at each health facility.

All participating Local Champions will provide evidence of trial specific training to their national Hub. All members of the research team at health facilities will also be required to sign the E-MOTIVE Site Signature and Delegation Log, which details which tasks have been delegated to them by the Local Champion.

9.2. Monitoring

On-site Monitoring

[figure not shown]
Monitoring visits and observations of healthcare providers managing real life vaginal births will also be conducted in health facilities during the baseline and intervention phases (both in sites randomised to the intervention and control groups) and in health facilities participating in the adaptive cycles. These will include observing the facility readiness for managing PPH and healthcare provider's treatment of postpartum haemorrhage if PPH occurs. An observation guide has been developed for use in health facilities participating in the adaptive cycles and health facilities randomised to the intervention group. A separate observation guide has been developed for use in health facilities during the baseline phase and in health facilities randomised to the control group. Observations of vaginal births will be conducted in intervention and control facilities at 1 or 2 time points during the study.

Additional on-site monitoring is carried out as required following trial specific risk assessment and as documented in the monitoring plan. The monitoring of spoke facilities will be conducted by the Hubs; the Hubs will be monitored by BCTU.

Any monitoring activities will be reported to the central trials team at BCTU and any issues noted will be followed up to resolution. Additional on-site monitoring visits may be triggered, for example by poor CRF return, poor data quality, or poor compliance with the E-MOTIVE intervention.

If an on-site monitoring visit is planned, the Hub trial team will contact the health facility to arrange a date for the proposed visit and will provide the health facility with written confirmation.

Figure 6 Hub and spoke organization model for the E-MOTIVE study.

Investigators will allow the Hub staff access to source documents as requested. During on-site monitoring visits the source data contained in source documents e.g., patient notes will be checked by the Hub team to ensure data are legible, original, accurate and well maintained.

Central Monitoring

E-MOTIVE trial staff from BCTU will be in regular contact with the Hub research teams to check on progress and address any queries that they may have.

Hub trial staff will check CRFs from the spoke facilities for compliance with the protocol, data consistency, missing data and timing. Hubs will send spoke facilities data queries for missing data or clarification of inconsistencies or discrepancies. BCTU will centrally monitor data received from the Hubs. More detailed monitoring processes will be detailed in the Monitoring Plan.

9.3. Audit and Inspection

National Principal Investigators and Local Champions will permit trial-related monitoring, regulatory inspections, audits, and ethical review at their site. The investigator will comply with these visits and any required follow up. If there are any externally-conducted inspections, Hubs are requested to notify BCTU in advance of any relevant inspections of the Hub site.

9.4. Notification of Serious Breaches

The Sponsor of the trial is responsible for notifying the regulatory bodies in writing of any serious breach of the conditions of the trial protocol, within 7 days of becoming aware of that breach.

For the purposes of this regulation, a “serious breach” is a breach which is likely to effect to a significant degree:

- the safety or physical or mental integrity of the women giving birth in the study facilities;
- the scientific value of the trial.

Hubs must notify the BCTU and Spokes are therefore requested to notify the Hub, of any suspected trial-related serious breach of the trial protocol. Where BCTU is investigating whether or not a serious breach has occurred, sites are requested to provide sufficient information to report the breach to the regulatory bodies where required and in undertaking any corrective and/or preventive action.

Any major problems identified during monitoring may be reported to BCTU, the TSC and the relevant regulatory bodies.

10. END OF TRIAL DEFINITION

The end of trial is defined as the final data capture from all participating health facilities. This will ensure completion of data collection, data input and analysis. The E-MOTIVE Trials Office at BCTU will notify each Hub that the trial has ended within 90 days of the end of trial and it will be their responsibility to notify the regulatory bodies of that country as relevant. A summary report will be sent to each Hub for submission to the regulatory bodies within 12 months of the end of the trial (if required).

11. STATISTICAL CONSIDERATIONS

11.1. Sample Size

Following issues around study data collection, and in discussion with the funder and the independent TSC and DMC committees, the study was reduced from 24 months to 16 months. Below, we outline the original sample size calculation and present the updated sample size calculation.

Original sample size calculation

Assuming there are 80 health facilities in the trial, evenly split across the intervention and control groups, with an average number of 192 births per health facility per month, the anticipated total sample size for the study (running for 22 months) would be 337,920 ($=80*192*22$). The number of health facilities (80) has been inflated by 10% to allow for drop out from the number of health facilities required (72). This sample size is expected to be sufficient to provide approximately 90% power at 5% significance (two-sided) to detect a change from 2% to 1.5% (25% relative reduction) in the primary outcome, after allowing for clustering and for varying cluster sizes and across most realistic scenarios. Below, we describe this calculation in more detail, firstly providing the rationale for the choice of these key values, and then outlining the methodology used to calculate the sample size. We provide details of the sensitivity of power to any changes in these key design parameters.

In the control condition, we expect the prevalence of the primary composite outcome to be around 2%. This prevalence is informed by the prevalence of a similar outcome based on analysis of the CHAMPION trial⁴ and we have considered sensitivity to this prevalence between 1.5% and 4%.

A relative risk reduction of 25% was considered to be a clinically meaningful difference to detect, though smaller reductions could also be worthwhile. Under some scenarios (such as a high value of the ICC) this target effect size might not be detectable at 90% power, and so we therefore consider a larger target effect size to demonstrate the size of effect size that can be demonstrated under these less conservative other scenarios. We have thus considered sensitivity to the power for a relative reduction of 20% and 30%.

Sample size calculations have allowed for the clustered nature of the design through the intra-cluster correlation (ICC). As recommended, values for the ICC have been informed through a combination of the literature and analysis of available data on a similar set of outcomes. Analysis of the CHAMPION trial⁴ found an ICC of 0.03 (95% CI: 0.02 to 0.05) for a similar composite outcome of PPH \geq 1000 ml, laparotomy and maternal death. This ICC was estimated using a linear mixed regression model and so is on the proportions scale as is appropriate for a sample size calculation. As the literature suggests, rare clinical outcomes tend to have small ICCs, for this reason we have considered an extended range for the ICC, from 0.001 to 0.05, with an expected ICC of 0.02.

To allow for variations in clustering over time, we have allowed for a cluster by period random effect. This has been incorporated in the sample size calculations using the cluster autocorrelation (CAC).^{15,16} There is limited information from the literature on likely values of the CAC. Using data from the CHAMPION trial⁴, we created two 11-month periods, which match the planned study design. From this, we estimated a CAC of 0.97. No current methodology exists to calculate a confidence interval for this value. We have chosen to consider sensitivity to the CAC between the values of 0.95 and 1.0.

Survey data from health facilities that was collected to obtain information on the number of births per health facility. From this survey data, we calculated an average number of births per health

facility per month of 192. The health facilities varied in size. We have estimated a coefficient of variation of cluster sizes of 0.5 and have allowed for this in our sample size calculations using a conservative correction.¹⁷ [Rutherford 2015].

The methods to calculate the sample size in a parallel CRT with a baseline period have been described fully by Hooper and Bourke.^{15,16} These methods have been implemented in an RShiny App (<https://clusterrcts.shinyapps.io/rshinyapp/>), used to inform the sample size for this trial.

Table 1 provides information on the expected level of power across the range of parameters outlined above. These suggest that the study has at least 80% power in almost all likely scenarios to detect a 25% relative risk reduction in the composite primary outcome from 2% to 1.5% (**Table 1**). If the ICC is at the upper limit (0.05), the study would have more than 80% power to detect a relative risk reduction of 30% in the composite primary outcome from 2% to 1.5% under every scenario considered except one (ICC=0.05 and CAC=0.95).

Table 1: Original estimates of the power with changes to key design parameters.

			RR = 20%			RR = 25%			RR = 30%		
			Control Prevalence								
			1.5 %	2.0 %	4.0 %	1.5%	2.0%	4.0%	1.5%	2.0%	4.0%
CAC = 0.95	IC	0.00									
		1	96.4	99.2	99.9	99.6	99.9	99.9	99.9	99.9	99.9
		0.02	54.6	67.1	92.9	68.1	80.3	98.0	84.1	92.8	99.8
CAC = 0.97	C	0.05	30.8	39.2	67.3	38.9	49.3	79.1	53.3	65.7	92.1
		0.00									
		1	96.8	99.3	99.9	99.7	99.9	99.9	99.9	99.9	99.9
CAC = 1.00	IC	0.02	67.8	80.1	97.9	81.9	91.4	99.7	93.8	98.2	99.9
		0.05	43.0	54.2	83.8	54.4	66.8	92.8	71.2	83.0	98.6
		0.00									
CAC = 1.00	C	1	97.4	99.9	99.9	99.6	99.9	99.9	99.9	99.9	99.9
		0.02	95.8	98.9	99.9	99.7	99.9	99.9	99.9	99.9	99.9
		0.05	95.4	98.8	99.9	99.9	99.9	99.9	99.9	99.9	99.9

Note: Power has been calculated assuming 72 health facilities, with an average number of 192 births per month (22 month study), and a coefficient of variation of cluster sizes of 0.5. CAC: Cluster autocorrelation; ICC: Intra cluster correlation. RR = Risk reduction

Updated Sample Size Calculation

In October 2021, a revised sample size calculation was performed, based on the study shortening from 24 months to 16 months (allowing for a 2-month transition period). As part of this, we evaluated some of the parameters made in the earlier calculation using estimates from the accrued baseline data (collected from October 2020 to September 2021) in sites with high quality data.

Assuming there are 80 health facilities in the trial, evenly split across the intervention and control groups, with an average number of 192 births per health facility per month, the anticipated total sample size for the study (running for 14 months) would be 215,040 (=80*192*14). The number of health facilities (80) has been inflated by 10% to allow for dropout from the number of health facilities required (72).

Table 2 provides information on the expected levels of power for a 16-month study (two 7-month periods and a 2-month transition period) across the range of parameters described earlier. These suggest that the study has at least 90% power at 5% significance (two-sided) to detect a 30% RRR for most scenarios after allowing for clustering and for varying cluster size. The study will have over 90% power to detect smaller RRR if the ICC is close to the lower bound (0.001), the CAC is at the upper bound (1.0), or the prevalence of the study is relatively large (4.0%).

Table 2: Estimates of the power with changes to key design parameters.

			RR = 20%			RR = 25%			RR = 30%		
			Control Prevalence								
			1.50 %	2.00 %	4.00 %	1.50 %	2.00 %	4.00 %	1.50 %	2.00 %	4.00 %
CAC = 0.95	ICC	0.001	86.8	94.5	99.9	97.4	99.5	99.9	99.7	99.9	99.9
		0.02	43.2	54.4	84	62	74.6	96.3	78.8	89.1	99.5
		0.05	24.8	31.6	56.1	36.8	46.7	76.4	50.6	62.7	90.3
		0.001	87.5	95	99.9	97.6	99.5	99.9	99.8	99.9	99.9
		0.02	53.9	66.3	92.5	74.1	85.5	99.1	88.8	95.7	99.9
		0.05	34.1	43.4	72.7	50.2	62.4	90.1	66.8	79.1	97.7
CAC = 0.97		0.001	89.7	96.2	99.9	98.3	99.7	99.9	99.9	99.9	99.9
		0.02	83.7	92.1	99.9	95.9	99	99.9	99.5	99.9	99.9
		0.05	83	92.6	99.9	96.2	99.1	99.9	99.4	99.9	99.9
CAC = 1.00		0.001	89.7	96.2	99.9	98.3	99.7	99.9	99.9	99.9	99.9
		0.02	83.7	92.1	99.9	95.9	99	99.9	99.5	99.9	99.9
		0.05	83	92.6	99.9	96.2	99.1	99.9	99.4	99.9	99.9

Note: Power has been calculated assuming 72 health facilities, with an average number of 192 births per month (14-month study), and a coefficient of variation of cluster sizes of 0.5. CAC: Cluster autocorrelation; ICC: Intra cluster correlation. RR = Risk reduction

Analysis of the baseline data found a prevalence of the primary outcome of 3.6% (95% CI: 3.4% to 3.8%) and an ICC of 0.018 (95% CI: 0.01 to 0.034). With large prevalence (4.0%), the study would have over 90% power to detect a 20% RRR for most likely scenarios (Table 2). A re-estimation of the CAC using two 7-month periods in CHAMPION data found a CAC of 0.99. With a CAC of 1.00, the study would have over 90% power to detect a 20% RRR for most likely scenarios.

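### Protocol 11.1 and SAP 4.7 overstate power for relative reductions below 30%: nine cells of their own table meet a stated condition yet fall under 90%

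*Protocol*

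**What the plan says.** The updated calculation in Protocol 11.1 first states that the study has "at least 90% power at 5% significance (two-sided) to detect a 30% RRR for most scenarios". The next sentence turns to smaller reductions: "The study will have over 90% power to detect smaller RRR if the ICC is close to the lower bound (0.001"). It adds two alternatives, "the CAC is at the upper bound (1.0), or the prevalence of the study is relatively large (4.0" per cent). Table 2, titled "Estimates of the power with changes to key design parameters", follows. It gives power for relative reductions of 20, 25 and 30%, so the smaller reductions it covers are 20 and 25%.

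After the table, two further sentences return to the 20% reduction, one for 4% prevalence and one for CAC 1.00. Both limit the claim of over 90% power to most of the likely settings.

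SAP 4.7 carries the same sentences. Its power table has the same entries and is printed as Appendix Table E8 (SAP 4.7 calls it E7).

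**The concern.** The sentence on smaller reductions has no qualifier, and it joins its three conditions with an or. Read plainly, meeting any one of them guarantees over 90% power for a reduction below 30%. The table beside it does not show that. The 4% condition matters most. It is the grid value closest to the baseline prevalence of 3.6%, and it is where the shortfall is largest. Protocol 11.1 also says that reductions smaller than 25% could be worth having, so a reader has reason to want the correct power at 20%.

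**Working it through.** **Step 1. Read the table against the sentence.** The grid is 3 ICCs × 3 CACs × 3 prevalences = 27 cells per reduction. Cells meeting none of the conditions number 2 × 2 × 2 = 8, so 27 − 8 = 19 cells per reduction meet at least one. Those below 90% are:

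| Reduction | Prevalence | ICC | CAC | Table 2 (%) | Recomputed (%) |
|---|---|---|---|---|---|
| 20% | 1.5% | 0.001 | 0.95 | 86.8 | 86.8 |
| 20% | 1.5% | 0.001 | 0.97 | 87.5 | 87.5 |
| 20% | 1.5% | 0.001 | 1.00 | 89.7 | 88.7 |
| 20% | 1.5% | 0.02 | 1.00 | 83.7 | 82.9 |
| 20% | 1.5% | 0.05 | 1.00 | 83 | 83.7 |
| 20% | 4% | 0.02 | 0.95 | 84 | 84.0 |
| 20% | 4% | 0.05 | 0.95 | 56.1 | 56.1 |
| 20% | 4% | 0.05 | 0.97 | 72.7 | 72.7 |
| 25% | 4% | 0.05 | 0.95 | 76.4 | 76.4 |

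That is 8 of 19 cells at 20% and 1 of 19 at 25%. The third row meets two conditions and is counted once. At 25%, ICC 0.001 holds in all nine cells (minimum 97.4%), CAC 1.00 in all nine (minimum 95.9%), and 4% prevalence in eight of nine.

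**Step 2. Rule out misprints by reproducing the table.** Inputs from Protocol 11.1: "Power has been calculated assuming 72 health facilities, with an average number of 192 births per month (14-month study"), "a coefficient of variation of cluster sizes of 0.5", "two 7-month periods and a 2-month transition period", facilities "evenly split across the intervention and control groups", and a two-sided 5% level. This gives 36 facilities per arm and m = 192 × 7 = 1,344 births per facility and period. The documents cite the method but do not print the formula. The form below is assumed because it fits the table:

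- M = m(1 + 0.5²) = 1,680
- D = 1 + (M − 1) × ICC
- r = M × ICC × CAC / D
- v = mean of p₁(1 − p₁) and p₂(1 − p₂)
- Var = [2v / (36m)] × D × (1 − r²)
- Power = Φ(|p₁ − p₂| / √Var − 1.96)

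Example: 4% to 3.2%, ICC 0.05, CAC 0.95.

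- D = 1 + 1,679 × 0.05 = 84.95
- r = 79.8 / 84.95 = 0.9394, so 1 − r² = 0.1176
- v = (0.0384 + 0.030976) / 2 = 0.034688
- Var = [0.069376 / 48,384] × 84.95 × 0.1176 = 1.432 × 10⁻⁵, so the standard error is 0.003784
- Power = Φ(0.008 / 0.003784 − 1.96) = Φ(0.154) = 56.1%, as printed

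All 81 cells reproduce within 1 point (largest difference 0.98, mean 0.07). All nine exceptions stay below 90%.

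**Step 3. Power at the trial's own baseline estimates** (3.6%, ICC 0.018), same formula:

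| Reduction | CAC 0.95 | CAC 0.97 | CAC 0.99 | CAC 1.00 |
|---|---|---|---|---|
| 25% | 95.6 | 98.7 | 99.9 | 100.0 |
| 20% | 82.4 | 91.1 | 97.9 | 99.5 |

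**The case against.** The strongest defence has four parts.

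- **The qualifier carries over.** The preceding sentence, on the 30% reduction, speaks of most scenarios, and with that carried over the text would fit the table. But the authors write a similar qualifier again in each of the two later sentences on 20%. They supplied it where they meant it, and this sentence has none.
- **Smaller means only the 25% target.** The text does not say so. If it did, the ICC and CAC conditions would hold in full, but the 4% condition would still fail once (76.4%).
- **The exceptions are unlikely.** This largely stands. Five of the nine are at 1.5% prevalence, well below the baseline interval of 3.4 to 3.8%. Three more need ICC 0.05, above the baseline interval of 0.01 to 0.034. The remaining one (84%) is at 4%, just above the prevalence interval, with the protocol's expected ICC of 0.02. Its CAC of 0.95 is below both CHAMPION estimates (0.97 and 0.99) but inside the range the protocol chose to examine. The defence does not make 4% prevalence sufficient on its own: at 4% and ICC 0.034, power for a 20% reduction is 69.0% at CAC 0.95 and 83.1% at CAC 0.97.
- **The table is printed in both documents.** True, and no figure is hidden. It limits the harm but does not make the sentence correct.

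A reader might also infer that this sentence justified shortening the study, or that a null result would be misread as well powered. The documents support neither. The protocol's amendment summary bases the shortening on more sites and a higher outcome rate, with the aim of detecting the difference originally planned, which is 25%. Protocol Appendix A reports a 60% reduction in the four African countries, so a null result did not arise.

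**Conclusion.** The sentence claims power that the design does not have in every setting it covers. The shortfall against 90% is at most 3.2 points under ICC 0.001 (90 − 86.8), 7 points under CAC 1.00 (90 − 83) and 33.9 points under 4% prevalence (90 − 56.1), all at a 20% reduction. At 25% it is 13.6 points in a single cell (90 − 76.4). Because the later sentences qualify two of the three conditions at 20%, the sections are also internally inconsistent.

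It would be wrong to conclude that the trial is too small or that the table is in error. The table reproduces, and the 25% target has at least 95.6% power at the baseline point estimates for CAC 0.95 and above. That last figure rests on the formula in the working and on the point estimates. At the upper ICC limit of 0.034 with CAC 0.95 and 3.6% prevalence it is 83.9%. The contradiction itself needs only the printed table.

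**What to change.** In Protocol 11.1 and SAP 4.7, replace the sentence on smaller reductions with:

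> For a 25% RRR, power exceeds 90% at ICC 0.001 or CAC 1.00, and at 4% prevalence except with ICC 0.05 and CAC 0.95 (76%). For a 20% RRR, power exceeds 90% at ICC 0.001 or CAC 1.00 only if prevalence is at least 2%, and at 4% prevalence only with ICC 0.001, or ICC 0.02 and CAC of at least 0.97, or CAC 1.00.

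Optionally, add the power at 3.6% prevalence and ICC 0.018 from step 3 of the working, which neither document gives.

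The cost is two sentences in each document and a less favourable statement at 20%. The sample size, design and analysis do not change.
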